The goal of Part A is to determine the prevalence of each biomarker and the overlapping frequency of biomarkers (primary objective), which will guide on-going screening for selecting biomarker positive patients for the clinical trial to be conducted in part B. The association between biomarker positivity and the patient clinical and pathological features will be studied (secondary objective) to guide the selection process. In addition, the effectiveness of prescreening locally and nationally will be estimated (secondary objective). Interim analyses will be conducted after 250 and 500 screened samples, before the final analysis, to inform ongoing screening strategies. We will compare and contrast these with the data available from planned and ongoing analyses of tissue microarrays. With 700 samples, the maximum width (distance from the lower limit to the higher limit) of 95% confidence interval for the prevalence of a biomarker will be 0.075.

Biomarker prevalence and its 95% (exact) confidence interval (CI) among the screening patients and for different histologies will be reported. Overlapping frequency and its 95% CI between biomarkers among the screening patients and for different

histologies will also be reported. The association between biomarker positivity and clinical/pathological features will be assessed using chi-square test, or Fisher's exact test if necessary, with the features including histology, age at diagnosis of current lung cancer (using age groupings as a categorical variable where necessary), age at diagnosis of metastatic lung cancer, race, sex, current stage, sites of metastatic disease at diagnosis, smoking status, EGFR, KRAS and ALK status. Biomarker prevalence will be reported for each category of features significantly associated with biomarker prevalence. We will determine the impact of biomarker results on prognosis generating Kaplan-Maier survival curves for overall survival using log-rank testing to compare the survival distributions between marker positive and negative patients for each biomarker. In addition, we will determine the impact of the biomarker results on sensitivity or resistance to standard chemotherapies and patterns of metastatic spread as we have done before (Camidge et al, 2011; Doebele et al, 2012).

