
5.5 Estimates on numbers needed to screen

Part A: The estimated size of Part A is based on literature and tissue microarray data suggesting the total numbers required to screen in order to identify sufficient marker positive patients to populate each of the different cohorts in Part B. Multiple different histological subtypes of lung cancer exist (Travis et al, 1999). Although proportions of the different histologies may differ between countries and be altering over time, for the purposes of sizing estimates we have assumed, based on literature and internal CU data that 88% of lung cancer is NSCLC and 12% SCLC and that 40% of NSCLC represents adenocarcinoma, 25% squamous carcinoma, 10% large cell and 25% other/not otherwise specified (NOS) (Travis et al, 1999). In the absence of additional data, we have also assumed that the prevalence of any given marker in the large cell/other/NOS category will reflect a population consisting of 2/3rds adenocarcinoma and 1/3rd squamous. All lung cancer histologies (NSCLC and SCLC) other than carcinoid will initially be screened in this trial for FGFR1 related biomarkers, and then RET FISH testing will be conducted in FGFR1 double negative cases with either adenocarcinoma or NOS histology when covered as SOC. However, per NCCN and CAP guidelines adenocarcinoma patients will require prior EGFR and/or ALK testing and patients with either an EGFR mutation or ALK rearrangement will be excluded. If patients of other histologies are known to be either EGFR mutant or ALK+, they too will be excluded. If patients known to be wildtype for several other drivers are also prioritized for screening this potential enrichment effect will be even more marked. However, of note our preclinical data shows the potential for FGFR related biomarkers to overlap with some KRAS mutant cases and consequently preselection of KRAS wildtype cases is not required. As data emerge this trial and other sources emerge on the prevalence of these different abnormalities, more focused screening e.g. by different histological subtypes or smoking status, for specific biomarkers may be adopted.

Based on literature and preliminary SPORE TMA data we have assumed the following:

- FGFR1 SISH will be positive in 16% squamous cancers (100% will also be ISH+ve) and 11% adenocarcinomas (0% will be ISH+ve).
- FGFR1 ISH will be positive in 43% squamous cancers (50% will also be SISH+ve) and 11% adenocarcinomas (0% will be SISH+ve)

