
given histology, molecular or smoking status have been screened without identifying a single positive case.

Excess marker positive patients identified beyond the initial cohort accrual targets, will be directed towards additional expansion of cohorts (following additional support) if evidence of $ORR \geq 40\%$, other studies or remaining standard therapies as appropriate, while generating a larger natural history database relating to *FGFR1/RET* biology.

See Figures 13-15 (schemas for expected frequencies) and Table 10 (estimated screening accruals and positives per year) for additional details.

FIGURE 13

*carcinoid excluded from all tested categories

All lung cancer (estimates)*

Adeno (40% NSCLC)	Squamous (25% NSCLC)	Large cell/NOS (35% NSCLC)	Small cell (12% LC)
-------------------	----------------------	----------------------------	---------------------

CU external/internal lung cancer patients screened for FGFR1 SISH and ISH

Adeno (excluding ALK+ or EGFR mt)	Squamous	Large cell/NOS	Small cell
-----------------------------------	----------	----------------	------------

CU external lung cancer patients screened for RET (All FGFR1 SISH and ISH negative)

Adeno (excluding ALK+ or EGFR mt)	Large cell/NOS
-----------------------------------	----------------

CU internal lung cancer patients screened for RET (All FGFR1 SISH and ISH negative and 'pan' negative by SNaPshot, ALK/ROS1/MET FISH) ~ approx 20 pts/year meeting these criteria

Adeno	Large cell/NOS
-------	----------------

FIGURE 14

CU external/internal lung cancer patients screened for FGFR1 SISH and ISH

Adeno (excluding ALK+ or EGFR mt)	Squamous	Large cell/NOS	Small cell
-----------------------------------	----------	----------------	------------

SISH+ISH-ve Estimated 8% NSCLC (all adeno or adeno-behaving NOS), 6% SCLC
SISH-veISH+ Estimated 16% (approx 50:50 adeno:squame)
SISH+ISH+ Estimated 6% (all squamous or squamous-behaving NOS)

Assumptions: FGFR1 SISH will be positive in 16% squamous cancers (100% will also be ISH+ve) and 11% adenocarcinomas (0% will be ISH+ve)
FGFR1 ISH will be positive in 43% squamous cancers (50% will also be SISH+ve) and 11% adenocarcinomas (0% will be SISH+ve).
FGR1 SISH will be positive in 6% SCLC (frequency and relationship to ISH unknown, assume zero/none for estimates).
Large cell/NOS behaves as if 66% adeno, 33% squamous
ALK (4%), EGFR (10%), FGFR1 SISH/ISH (22%) mutually exclusive in adeno
88% LC = NSCLC, 12% SCLC

FIGURE 15

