10.0 ANALYSIS PLAN AND DATA CAPTURE

10.1 Estimated patient numbers

We aim to screen 700 patients in total in Part A (see Section 5 for details of calculation)

Study requirements, in terms of Part B enrollments: Accruing 13 patients for each 12 that will be evaluable.

22 (20 evaluable) patient FGFR1 double negative cohort (up to additional 36 across all cohorts, but likely mostly within FGFR1 double negative cohort if altered dosing required)

13 patient FGFR1 SISH+ve and ISH+ve cohort

13 patient FGFR1 SISH+ve and ISH-ve cohort

13 patient FGFR1 SISH-ve and ISH+ve cohort

13 patient RET+ve cohort

Estimate 74 patient (inc non-evaluable) on treatment study, up to 100 if additional biomarker cohorts are added to be explored.

Excess marker positive patients identified beyond the initial cohort accrual targets, will be directed towards additional expansion of cohorts (following additional support) if evidence of $ORR \geq 40\%$, other studies or remaining standard therapies as appropriate, while generating a larger natural history database relating to *FGFR1/RET* biology.

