10.2 Part A Analysis Plan

The goal of Part A is to determine the prevalence of each biomarker and the overlapping frequency of biomarkers (primary objective), which will guide on-going screening for selecting biomarker positive patients for the clinical trial to be conducted in part B. The association between biomarker positivity and the patient clinical and pathological features will be studied (secondary objective) to guide the selection process. In addition, the effectiveness of prescreening locally and nationally will be estimated (secondary objective). Interim analyses will be conducted after 250 and 500 screened samples, before the final analysis, to inform ongoing screening strategies. We will compare and contrast these with the data available from planned and ongoing analyses of tissue microarrays. With 700 samples, the maximum width (distance from the lower limit to the higher limit) of 95% confidence interval for the prevalence of a biomarker will be 0.075.

Biomarker prevalence and its 95% (exact) confidence interval (CI) among the screening patients and for different histologies will be reported. Overlapping frequency and its 95% CI between biomarkers among the screening patients and for different histologies will also be reported. The association between biomarker positivity and clinical/pathological features will be assessed using chi-square test, or Fisher's exact test if necessary, with the features including histology, age at diagnosis of current lung cancer (using age groupings as a categorical variable where necessary), age at diagnosis of metastatic lung cancer, race, sex, current stage, sites of metastatic disease at diagnosis, smoking status, EGFR, KRAS and ALK status. Biomarker prevalence will be reported for each category of features significantly

associated with biomarker prevalence. We will determine the impact of biomarker results on prognosis generating Kaplan-Maier survival curves for overall survival using log-rank testing to compare the survival distributions between marker positive and negative patients for each biomarker. In addition, we will determine the impact of the biomarker results on sensitivity or resistance to standard chemotherapies and patterns of metastatic spread as we have done before (Camidge et al, 2011; Doebele et al, 2012).

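### Part A tests each clinical feature against the markers without accounting for histology, so a feature that merely tracks histology can appear related to FGFR1 ISH

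*Combined protocol and SAP*

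**What the plan says.** Section 10.2, repeated in the synopsis, covers the Part A secondary objective on features associated with marker positivity: "The association between biomarker positivity and clinical/pathological features will be assessed using chi-square test", with Fisher's exact test as the fallback. The list holds histology, two ages at diagnosis (grouped where necessary), race, sex, stage, metastatic sites, smoking and EGFR, KRAS and ALK status. No model, stratum or covariate is named. The reporting rule begins "Biomarker prevalence will be reported for each category of features significantly" and continues to those associated with prevalence; no significance level is stated. Prevalence with exact intervals "among the screening patients and for different histologies will be reported", which is descriptive. Overall survival is compared by log-rank test between marker-positive and marker-negative patients, with no strata. The only multivariable analysis in the plan is in Part B (Section 10.3) and compares one biomarker with another.

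The results have a stated use: "The association between biomarker positivity and the patient clinical and pathological features will be studied (secondary objective) to guide the selection process". Interim analyses at 250 and 500 samples are to inform screening strategy. Section 5.5 and the footnote to Table 10 contemplate focusing screening by histology or smoking status.

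Section 5.5 assumes: "FGFR1 ISH will be positive in 43% squamous cancers (50% will also be SISH+ve) and 11% adenocarcinomas". SISH is put at 16% of squamous and 11% of adenocarcinoma. Figure 14 places SISH+ISH+ only in squamous or squamous-behaving NOS, and SISH+ISH- within NSCLC only in adenocarcinoma or adenocarcinoma-behaving NOS.

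**The concern.** Where the marker rate depends on histology and a feature's distribution also depends on histology, the two are associated marginally even if the feature carries no information once histology is known. A one-at-a-time chi-square test cannot tell this apart from a feature that adds something within histology. The secondary objective could then list smoking or sex as correlates of ISH when they only stand in for squamous disease, and screening could be narrowed on a feature that adds nothing to a variable already in hand.

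The direction also depends on the marker group. SISH+ISH+ is expected only in squamous-like disease and NSCLC SISH+ISH- only in adenocarcinoma-like disease, so the same feature could seem to favour one Part B cohort and disfavour another with no effect of its own. The log-rank comparison is exposed in the same way if prognosis differs by histology.

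**Working it through.** **The plan's own figure.** The only design figure for Part A is a maximum 95% interval width of 0.075 at 700 samples. The exact interval at 350/700 has width 0.0754, so it reproduces. It concerns precision of a prevalence; no power or significance level is given for the association tests.

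**Inputs from the documents.** "We aim to screen 700 patients in total in Part A" (Section 10.1). Section 5.5: 88% NSCLC and 12% SCLC; NSCLC is 40% adenocarcinoma, 25% squamous and 35% large cell/other/NOS; the last behaves as 2/3 adenocarcinoma and 1/3 squamous; 14% of adenocarcinomas (10% EGFR, 4% ALK) are excluded. Figure 14 takes ISH in SCLC as zero for its estimates.

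Per 100 lung cancers:
- Adenocarcinoma-like: 35.2 × 0.86 + 30.8 × 2/3 = 50.8
- Squamous-like: 22 + 30.8 × 1/3 = 32.3
- SCLC: 12
- Total: 95.1

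Scaled to 700 screened, that is 374, 238 and 88.

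**Squamous v adenocarcinoma, by marker.**
- ISH: 43/11 = 3.9-fold
- SISH: 16/11 = 1.45-fold
- Any FGFR1 marker: 43% v 22%, or 1.95-fold (all SISH+ squamous cases are assumed ISH+)
- SISH+ISH+: 16% v 0%
- SISH+ISH-: 0% v 11%, reversed

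**Assumptions, not in the documents.** Feature rates by histology; SCLC given the squamous feature rate; two-sided 5% level; no effect of the feature on the marker within adenocarcinoma-like, squamous-like or SCLC disease.

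**One case in full: ISH, smokers 75% of adenocarcinoma-like and 95% of the rest.**
- Smokers: 374 × 0.75 + 238 × 0.95 + 88 × 0.95 ≈ 590; non-smokers ≈ 110.
- ISH+ in smokers: (280.6 × 0.11 + 225.7 × 0.43)/590.2 = 21.7%.
- ISH+ in non-smokers: (93.5 × 0.11 + 11.9 × 0.43)/109.8 = 14.0%.
- Odds ratio 1.7; difference 7.65 points; standard error 4.19 points pooled, 3.72 unpooled.
- Probability of significance: Φ[(7.65 − 1.96 × 4.19)/3.72] = Φ(−0.15) = 0.44.

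**All cases, ISH, N=700.** Simulation, 20,000 runs per row; the crude column agrees with the formula above. The stratified column is a Cochran-Mantel-Haenszel (CMH) test by reported histology (adenocarcinoma, squamous, large cell/NOS, SCLC).

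| Assumed feature rate, adenocarcinoma v squamous | Crude test significant | Stratified test significant |
|---|---|---|
| Smoking 80% v 90% | 0.14 | 0.06 |
| Smoking 85% v 95% | 0.17 | 0.07 |
| Smoking 75% v 95% | 0.44 | 0.14 |
| Smoking 60% v 95% (extreme) | 0.81 | 0.30 |
| Sex-like 50% v 70% | 0.27 | 0.10 |
| Age-like 50% v 60% | 0.10 | 0.06 |
| No difference 50% v 50% | 0.05 | 0.05 |

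Stratifying on the true lineage instead of reported histology gives 0.05 throughout, so the remaining excess comes from the mixed large cell/NOS stratum.

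**Other markers, N=700.** For SISH the crude test is significant in 0.04 to 0.06 of trials in every scenario. For SISH+ISH- it is 0.16 to about 0.52 for smoking at 85%, 75% and 60% v 95%, in the opposite direction to ISH.

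**A caveat on SISH.** Section 5.5 is not self-consistent for squamous disease: half of 43% is 21.5% SISH+, against the stated 16%. At 21.5%, the 75% v 95% smoking case gives SISH+ in 14.3% of smokers and 11.9% of non-smokers, with pooled and unpooled standard errors 3.60 and 3.41 points. The probability of significance is then about 0.09, still small.

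**The case against.** The strongest reply is that a marginal association is not an error. The objective is to find features associated with positivity, a chi-square test addresses exactly that, and a crude association is real and predicts screening yield. When histology drives both variables, the marginal null is false and rejecting it is correct. This stands. It means the crude tables should be kept, and that the percentages above are not type I error rates of the planned test. They are the chance that a feature adding nothing within histology is listed as significant.

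The plan also tests histology itself and reports prevalence by histology, so readers will see the main driver. That helps, but it does not show whether smoking, sex or age adds anything within histology. Age is grouped only where necessary, so that point is minor. The analysis is secondary and touches neither primary objective.

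A reader might infer that screening would be cut automatically on these results. The documents do not support that. The only numeric rule allows a subgroup to be ruled out once at least 100 patients of a "given histology, molecular or smoking status have been screened without identifying a single positive case". That is not a p-value rule, and confounding would not trigger it: even in pure adenocarcinoma at 11% ISH+, the chance of no positive in 100 is 0.89^100, about 0.000009. What remains is the discretionary focusing of screening described in Section 5.5.

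**Conclusion.** The omission is real and worth correcting. Part A feature tests and the marker log-rank comparison take no account of histology, while the plan's own rates make histology a strong determinant of ISH and of the SISH/ISH groups, and the results are meant to guide selection.

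Size: for ISH at N=700, a feature with no within-histology effect is significant in about 14% to 44% of trials for smoking (81% in an extreme case), 27% for a sex-like feature and 10% for an age-like one. These figures rest on assumed feature rates by histology, on SCLC having zero ISH and squamous-like feature rates, and on the Section 5.5 mix. No size can be put on the log-rank comparison, because the documents give no survival by histology.

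Two stronger readings do not hold. A reader might infer that FGFR1 positivity in general differs four-fold by histology; that is true of ISH only. A reader might also infer that smoking, sex and age will certainly look marker-related. They can, but in all but the extreme smoking case the crude test is more often non-significant. Restricting the calculation to the 612 NSCLC cases raises the smoking figures to 21% to 67% and the sex-like figure to 43%, but Part A screens SCLC and Section 10.2 does not exclude it from these tests.

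**What to change.** In Section 10.2 and the synopsis:

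- Keep the crude chi-square/Fisher tables, labelled as descriptions of screening yield, and state the significance level used.
- For each marker separately (ISH, SISH, the SISH/ISH groups, RET), add a histology-adjusted analysis of the other features: logistic regression with histology (adenocarcinoma, squamous, large cell/NOS, SCLC) and continuous age, or a CMH or exact stratified test where counts are sparse.
- Stratify the marker log-rank test by the same histology groups.
- Use the within-histology results when considering narrowing screening by smoking, sex or age beyond histology, including at the 250- and 500-sample looks.

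The cost is wording. Section 5.2 already has a pathologist confirm the specific histology, so no new data are needed. Intervals will be slightly wider in sparse histologies. Some confounding will remain inside large cell/NOS if it is the assumed 2/3:1/3 mix: for smoking at 85%, 75% and 60% v 95%, stratification brings the ISH rejection rate to 0.07, 0.14 and 0.30, not to 0.05. The report should say so.

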responses are seen in the initial RET+ cohort but FGFR1+ responses or FGFR PD modulation have been noted at 45mg and 45mg appears acutely well tolerated per DLT criteria we will reconsider this logic and accrue an additional RET+ cohort at 45mg. If doses other than 45mg QD are explored, the number of patients in each biomarker selected cohort will be modified to include only those treated at the final ‘biologically selected dose’ (i.e. the tolerable dose associated with evidence of FGFR pathway pharmacodynamic modulation or of radiographic responses in FGFR biomarker selected cohorts) and the response rates in each biomarker selected cohort will be calculated within each cohort using only the number treated at this dose.

Objectives:

Primary:

Part A – To determine the prevalence of defined biomarkers in the screened patient populations.

Part B – To determine the objective response rate (ORR) (RECIST v1.1) to ponatinib at a ‘biologically selected dose’ in different molecularly defined cohorts of lung cancer.

Secondary:

Part A –

- 1) To determine the effectiveness of prescreening locally and nationally.
- 2) To determine the clinical and pathological features associated with biomarker positivity and negativity.

Part B –

- 1) To evaluate the safety, tolerability, and adverse event profile of ponatinib in patients with advanced lung cancer.
- 2) To determine the progression free survival (PFS), pattern of failure (CNS vs. extra-CNS) and response duration (in patients who achieve an objective response) of ponatinib in molecularly defined cohorts of patients with advanced lung cancer treated at the ‘biologically selected dose’.
- 3) To compare the ORR in biomarker positive cohorts to the FGFR1 double negative cohort.

Tertiary/Exploratory:

- 1) To explore additional molecular mechanisms of initial sensitivity and resistance to ponatinib in patients with advanced lung cancer, including but not limited to addressing the impact of higher cutpoints/alternate patterns of FGFR1 copy number by SISH and mRNA levels by ISH on maximal percentage shrinkage per RECIST or PFS or duration of response in the FGFR1 copy number and/or mRNA positive cohorts; and the impact of FGF2 and/or 9 ligand mRNA levels by ISH on maximal percentage shrinkage per RECIST or PFS or duration of response in FGFR1 copy number and/or mRNA positive cohorts.

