5.3 Assessments specific to Part A

In order to assess the effectiveness of country-wide outreach and remote consenting for molecular testing we will track the number and location of patients registering via web and phone, the number suitable for molecular pre-screening after initial contact and remote consenting, the number with available tissue, the number with a positive result and the proportion of these who are then enrolled on the ponatinib intervention trial in Part B (Figure 13).

Figure 13: Data capture relating to Part A specific assessments in addition to marker positivity

Patients proceeding with molecular prescreen consenting - capture of key demographics (e.g. age at diagnosis, sex, histology, stage, smoking status, other molecular status, home State), ongoing capture of other therapies and benefit and overall survival
Archival FFPE specimen acquired? yes/no
Pathology review of specimen including prior documentation and molecular analyses
Lung cancer (non-carcinoid)? yes/no
If adenocarcinoma known EGFR/ALK wildtype? yes/no
Sufficient material for molecular analysis? yes/no
Trial marker positive? yes/no
Inform patient of result
Marker positive patient screens for trial Rx? yes/no (reasons)
Marker positive patient receives trial Rx? yes/no (reasons)

For patients who have a positive result but who do not enroll on the ponatinib trial, the patient, or their nominated contact, will be phoned to explore the reason for non-enrollment. Reasons will be categorized as financial barriers, fitness barriers, on alternative therapy, declined therapy, treatment based on biomarker result at another site, death, other (to be specified). Analyses will be descriptive in nature and will contrast this remote outreach methodology with the numbers and proportions seen through traditional direct clinical contact and local consenting at CU for the same trial.

We will define the natural history of the different biomarker positive subgroups, separate from their responsiveness to ponatinib. For example, we and others have previously demonstrated that ALK+ NSCLC is primarily, but not exclusively associated with adenocarcinoma histology, never or light smoking status, younger age of onset and absence of co-existent EGFR or KRAS mutations (Shaw et al,

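### Part A names only chi-square or Fisher's exact tests for age against marker positivity, with no age bands fixed; both ages should be tested as continuous variables

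*Combined protocol and SAP*

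**What the plan says.** The second secondary objective of Part A (Section 1) is "To determine the clinical and pathological features associated with biomarker positivity and negativity". Section 10.2, repeated in the synopsis, gives one method for it: the association "will be assessed using chi-square test, or Fisher's exact test if necessary". Eleven features follow. One is "age at diagnosis of current lung cancer (using age groupings as a categorical variable where necessary"; the next runs "age at diagnosis of metastatic lung cancer, race, sex, current stage", so the second age variable has no note on grouping at all.

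The number of bands and their boundaries are not stated. No t-test, rank test, trend test or regression is named for this objective. No significance level is given either, although the result decides what is shown: "Biomarker prevalence will be reported for each category of features significantly" associated with prevalence. Interim analyses after 250 and 500 samples are to inform screening. The planned size is given in Section 10.1: "We aim to screen 700 patients in total in Part A".

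**The concern.** Both named tests need categories, so a continuous feature has to be cut before it can be tested. Three things follow.

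- Cutting age loses part of the information in it.
- With three or more bands, chi-square ignores their order and spreads the test over several degrees of freedom.
- With no bands fixed, the cut can be chosen after seeing the data, which raises the false-positive rate.

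At stake is whether a real age association is found or a spurious one reported. Section 10.2 says the association results are meant to guide patient selection. The rarer the marker, the less power there is to spare: Table 10 expects only 20 RET-positive patients.

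**Working it through.** **The plan's own figure.** There is no power figure for this objective. The only Part A precision figure is a maximum 95% confidence interval width of 0.075 for a prevalence with 700 samples. It reproduces: the exact interval at 350/700 has width 0.0754. It says nothing about the age comparisons.

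**Inputs from the documents.**
- Any FGFR1 ISH-positive: 16% (SISH-negative, ISH-positive) + 6% (double positive) = 22% of 700 (Section 5.5, Figure 14).
- SISH+ISH+: 6% of 700, about 42 patients.
- RET positives in Table 10: 2+4+4+4 internal and 1+1+2+2 external = 20. Tested: 10+20+20+20 = 70 internal and 28+56+56+56 = 196 external = 266. So 20/266 = 7.5%.

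**Assumptions, since the documents give none.** Normally distributed age, log-odds of positivity linear in age, two-sided alpha 0.05, and odds ratios per SD of age as shown below.

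**Step 1: information kept by grouping.** For a normal variable cut into groups with shares p_j at boundaries c_j, and φ the standard normal density, the share kept under a small shift is Σ[φ(c_(j−1)) − φ(c_j)]²/p_j.
- Median split: 2 × φ(0)²/0.5 = 2/π = 64%.
- Tertiles 79%, quartiles 86%, quintiles 90%.
- A single 80/20 cut keeps 49%.

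**Step 2: large-sample power.** A continuous test with 80% power has noncentrality 7.85 on 1 df.
- Median split: 7.85 × 0.637 = 5.00 on 1 df gives 60.9%, a loss of 19.1 points.
- Quartiles: 7.85 × 0.861 = 6.76 on 3 df gives 57.3%, a loss of 22.7 points.
- A 1-df trend test on the same quartiles loses only 6.1 points. So with quartiles most of the loss comes from ignoring order, not from the cutting itself.

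**Step 3: simulation at the planned sizes.** Several thousand runs per setting, with the intercept set so that the prevalence equals the planned value. The continuous test is a t-test of age by marker status, close to the logistic regression test.

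| Marker | Odds ratio per SD | Continuous | Median split | Quartiles | Loss (points) |
|---|---|---|---|---|---|
| ISH+, 22% of 700 | 1.28 | 76% | 58% | 53% | 18 to 23 |
| RET, 7.5% of 266 | 2.0 | 83% | 62% | 59% | 21 to 24 |
| SISH+ISH+, 6% of 700 | 1.65 | 87% | 68% | 65% | 19 to 22 |

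A Wilcoxon rank test keeps nearly all the power of the continuous test: about 75%, 81% and 85% in the same three rows.

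**Step 4: how far this depends on the effect size.** For ISH+ with a median split, an odds ratio of 1.11 gives 20% v 14%, and 1.49 gives 99% v 93%. The loss is then about 5 to 7 points. With quartiles, the Step 2 method gives a loss of 7.9 points at 20% reference power.

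**Step 5: movable bands.** With no age effect, taking the best of five single cuts between the 30th and 70th percentiles gives a type I error of roughly 14% to 16% instead of 5%. The five cuts are an assumption; the plan does not exclude such a choice.

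**The case against.** The strongest reply is that the plan groups age only where needed, so it does not commit to grouping, and that a statistician would use an ordinary continuous test in practice. The wording does leave that room. But it names no such test, and neither named test accepts an ungrouped age, so the gap remains.

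Three stronger readings are tempting and are not supported.

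- A reader might infer that grouping throws away most of the information in age. Ordinary groupings keep 64% to 90%; more than half is lost only with a single very unequal cut, which the plan does not propose.
- A reader might infer that the whole secondary objective loses about 20 points of power. The loss applies to two of eleven features, the objective has no power target, and 20 points is near the top of the range for a median split.
- A reader might infer that a monotone age effect is what the protocol expects, because Section 5.3 lists "never or light smoking status, younger age of onset and absence of co-existent EGFR or KRAS mutations" as features of ALK-positive disease. That is an example about a different driver, and ALK-positive adenocarcinoma is excluded here. Section 6.3 describes the link between this study's markers and age as unknown.

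It is also fair that the enrichment rules in Section 5.5 mention histology, molecular status and smoking but not age, so the effect on selection is indirect. Reporting prevalence by category does need age bands, but for description rather than for the test.

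**Conclusion.** The point holds as a minor one. As written, the two age variables can be tested only after grouping, at cut-points that are not stated. The cost is about 18 to 24 points of power for those two comparisons when a continuous test would have roughly 75% to 90%. It shrinks to about 5 to 7 points (median split) when the effect is much weaker or stronger. These figures rest on a log-linear effect, normal ages, two-sided 0.05 and assumed odds ratios, none of which the documents supply. If the true age effect were strongly non-monotone, a grouped test could do better than a linear one. The open choice of bands is a separate weakness that does not depend on the effect size. Neither touches the primary prevalence estimates or Part B.

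**What to change.** In Section 10.2 and the synopsis, state that age at diagnosis and age at metastatic diagnosis will be tested as continuous variables, by logistic regression of marker positivity on age or by a two-sample rank test. State fixed age bands in advance and use them only for the descriptive prevalence table.

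The cost is one sentence in each place and no new data, since Section 5.3 already lists both ages for capture. The downside is that a linear term can miss a strongly non-monotone effect, so add a quadratic or spline term as a check.
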